1.3. Research questions and hypotheses, theoretical approach and methodology

RESEARCH QUESTION: Through a decentralized RCT investigating two digital interventions with differentiated levels of therapist-support, the goal is to expand knowledge about transdiagnostic relapse prevention strategies that can easily be scaled up and have the potential of cost-effectively reducing relapse rates for adolescents in an important phase of life. Alongside, collecting empirical

[figure not shown]
evidence for the association between repetitive negative thinking and relapse will increase knowledge regarding underlying mechanisms of relapse prevention strategies.

DESIGN: The trial is designed as a three-armed randomized single-blind open-label clinical trial (1:1:1) with stratification based on gender. It will not be possible to blind participants in the study due to the obvious differences between the interventions. We will investigate the effects of the “Tankevirus”-therapist-guided intervention and the “Tankevirus” smartphone app, respectively, and compare the effect of these transdiagnostic interventions to assessment only. All arms will be conducted in combination with care as usual. Assessments are done digitally, with no influence from the researcher. The primary endpoint of the trial will be analyzed blinded to treatment allocation. The trial will be preregistered with clinicaltrials.gov.

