INTERVENTIONS: “Tankevirus” is an award-winning psychological intervention developed for adolescents aged 16 and above, including a book, a mastery course, and a smartphone app. It is based on the principles of CBT to help individuals identify and challenge negative thought patterns that can lead to anxiety and depression. “Tankevirus” has been extensively evaluated. From 2017-2021, 50.000 students took part in the overarching “Tankevirus” School program, and 9 out of 10 thought the interventions were useful and would recommend it to a fellow student. The “Tankevirus” smartphone app is freely available, and within 16 months, it was downloaded by 26.000 adolescents. Based on patient reported outcome measures, 7 out of 10 reported improvements in overall health and increased quality of life. The app includes several components to increase engagement with the intervention material, which is a necessary prerequisite for digital mental health interventions to be effective (26), and smartphone apps which have elements built in to promote engagement are associated with larger effect sizes (29). In this project we will include two different formats of the “Tankevirus”-interventions, in addition to a control condition:

- **“Tankevirus” therapist-guided group intervention:** The intervention will be delivered by therapists having extensive experience with this age group in the form of 3 weekly 75-minutes sessions to groups of approximately 30-35 participants. An online GDPR-compliant webinar-platform including chat-options will be used (edumeet.org). Adolescents will remain anonymous to each other to decrease barriers to participation. The adolescents will book their preferred timeslot online. For the participants randomized to this intervention, a certain waiting period (~1 week) must be expected. We will keep record of number of days waiting for each person and include this as covariate in the analysis.
- **“Tankevirus” smartphone app:** The app will be downloaded to their personal smartphone, and the app will give push-notifications once new modules are released – every day for 3 weeks. The app has several procedures built in for engagement purposes but will not involve contact with a therapist. Usage data will be recorded to verify compliance. The app is developed in accordance with the requirements of the Norwegian Health Authorities and complies with data protection laws.

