participants. Our pre-inclusion assessments and inclusion criteria will be less comprehensive, allowing for more participants to be included. Presuming that the three birth cohorts in Norway comprises 150.000 adolescents aged 16-19. Of these, 5 % will currently have an anxiety disorder and 2% will have a depressive disorder as per diagnosis in specialized health care (45), amounting to approximately 10.500 potential participants. We would then need to recruit 4.7 % of this population (495/10.500) to complete this study. When considering that we require the adolescents who are in remission only, that they may have fulfilled the criteria at earlier ages, and that only a minority of adolescents are diagnosed and/or treated in specialized health care even when having profound symptom load (46), these numbers are conservative.

Attrition is another risk factor. The evidence in relation to decentralized trials and retention among adolescents is still scarce, and recommendations currently rely on the use of well-evidenced strategies (e.g., incentives, reducing barriers and burden, and investing in building positive relationships with participants) when engaging adolescents in longitudinal health studies (47). Hence, the adolescents will be issued a universal gift card worth 1200 NOK when they have completed their participation. Each assessment will be initiated by a prompt about how much it's pays to promote its completion. The therapists in the therapist-led interventional arm have extensive experience delivering these interventions to youths and are good at building positive relations. Due to the digitalized format, push notification will be used to promote engagement.

ETHICS: There is an inherent risk of relapse among these adolescents, and it will therefore be important to detect if their state deteriorates during the trial and offer them advice on how they can proceed to receive the adequate level of care. The contact information to the project group will always be available in the app. At all follow-ups, if a certain symptom load is detected, a pop-up message will appear, including our contact information and information about treatment providers. If CIDI 5.0 pre-assessment reveals an ongoing disorder, the adolescent will be advised on whom to contact for receiving adequate level of care and will not be included in this trial.

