3.2. Project organization and management

Project period: June 2025-June 2028.

Table 3: Gantt chart

Activity	Responsible	Year 1				Year 2				Year 3			
		Q1	Q2	Q3	Q4	Q1	Q2	Q3	Q4	Q1	Q2	Q3	Q4
Preparation													
Designing	RB, HB, KR, NIL, KBT												
Data protection	RB, KR												
Ethical approval	RB												
Preregistration	RB, NIL												
Piloting	RB, HB												
Recruiting patients	JRH, RB												
Data collection													
Interventions	BM, HB												
Follow-up	RB												
Statistical analysis													
Primary endpoint	RB, KR												
Exploratory analysis	RB												
Dissemination													
Publish inter.	NIL, RB, HB, KR												
Communication	RB, HB, JRH												

Through Nettskjema and Tjenester for sensitive data (TSD), the University of Oslo will provide research infrastructure for collecting informed consents digitally with MinID or BankID. This is the only identifiable information we will collect. The “Tankevirus” smartphone intervention is already developed and will be incorporated in a research platform allowing for all data to be collected in a streamlined, and anonymized manner. This app is currently being developed by Maths in Health and the anonymity of the platform will be assessed by SIKT for adherence to privacy regulations (GDPR).

References

1. World Health Organization. Mental Health of Adolescents 2021 [Available from: <https://www.who.int/news-room/fact-sheets/detail/adolescent-mental-health>].

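### Days waiting, recorded only for the therapist-guided arm but named as an analysis covariate, would reveal that arm to the one party the protocol says is blinded

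*Protocol*

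**What the plan says.** The DESIGN paragraph of protocol section 1.3 reads: "The trial is designed as a three-armed randomized single-blind open-label clinical trial (1:1:1) with stratification based on gender". It goes on: "It will not be possible to blind participants in the study due to the obvious differences between the interventions". It adds "Assessments are done digitally, with no influence from the researcher", and then "The primary endpoint of the trial will be analyzed blinded to treatment allocation".

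Under PRIMARY ENDPOINT in the same section, relapse is determined from PHQ-4 every two weeks, followed by the remaining PHQ-A items when the depression subscale is at or above the threshold. The participant completes all of these in the app.

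Under INTERVENTIONS, the entry for the therapist-guided group says that those randomised to it should expect to wait about a week, and continues: "We will keep record of number of days waiting for each person and include this as covariate in the analysis". No waiting period is described for the app arm or for assessment-only.

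Table 3 in section 3.2 lists two team members for the primary endpoint analysis. One of them is also listed for recruitment, with a colleague, and is the only person listed for follow-up. The other is listed for neither.

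**The concern.** Nobody independent of the participant rates the outcome, and the participant is not blinded. Digital capture removes interviewer influence but does not mask the person answering. The single-blind description therefore rests entirely on the analyst.

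A variable that takes real values in only one arm labels that arm. If it sits in the primary model, an analyst working with codes A, B and C can tell which one is therapist-guided. Any choice still open when the data are seen, for example how ongoing care is controlled for, could then be made with that arm known. The blind protects against exactly this, and the trial would be reported with a protection it did not have for comparisons that involve the therapist arm.

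**Working it through.** The protocol gives no figure on this point to reproduce. The check sets the statements side by side, with a small illustration.

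**1. Who is blinded?**
- Participants: no, stated in DESIGN.
- Outcome assessor: none separate from the participant (PRIMARY ENDPOINT).
- Analyst of the primary endpoint: yes, stated in DESIGN.

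The analyst is the only blinded role named.

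**2. What does days waiting reveal?** It arises after randomisation and is described for one arm. In the other two arms it would be zero or missing throughout. With three coded arms there are 3! = 6 ways to match codes to treatments. Once the therapist code is known, 2! = 2 remain: app and assessment-only are still interchangeable.

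**3. Could the marker be too faint to notice?** Assume, for illustration only, a Poisson wait with mean m days in the therapist arm, zero in the other arms, and 165 per arm (STATISTICAL POWER, section 1.3). The share of therapist-arm participants with a non-zero wait is 1 − exp(−m). The chance that no one in the arm has a non-zero wait, so that the code stays hidden, is exp(−165m).

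| Mean wait m (days) | Share with non-zero wait | Chance code stays hidden |
|---|---|---|
| 1 | 63.2% | 2.2 × 10⁻⁷² |
| 3 | 95.0% | 1.1 × 10⁻²¹⁵ |
| 7 (about the stated week) | 99.9% | effectively zero |

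The result does not depend on the exact mean. Anonymised data capture does not help, because the covariate itself carries the arm.

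**4. Which comparisons are affected?** Of the three pairwise contrasts, therapist versus app and therapist versus assessment-only include the revealed arm. App versus assessment-only does not. The first limb of the main hypothesis, therapist-guided against app, is among those affected.

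**5. What of the other arm-specific data?** App usage is recorded to verify compliance, and the CSQ-I goes only to the two intervention arms. Either could help to break the remaining codes if it were in the analyst's file. The protocol does not place either one there.

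**6. What does Table 3 show?** It shows who is responsible for each activity, not who can see allocation.

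**The case against.** The strongest reply is that the covariate sentence does not say which analysis it means. If it means a secondary one, the two statements can both be carried out. Coded files and staged release of variables are also normally settled in a statistical analysis plan, which was not available here. The first part stands as a condition on the finding. It does not remove the finding, because the sentence makes no exception for the primary analysis and the blinding statement is specific to it. The second part means that the absence of a data-release procedure is not itself a fault; the point is the conflict between two statements in the protocol.

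Three stronger readings are tempting, and the document does not support them.

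- A reader might infer that every code is broken as soon as the data are opened. That would need usage or CSQ-I data in the primary analyst's file, which is nowhere stated. All arms also use a research app for assessments, so some usage data could exist in every arm.
- A reader might infer that the Table 3 overlap, together with the safety provision "The contact information to the project group will always be available in the app", shows that the analyst knows allocation. It does not. Recruitment precedes randomisation and runs mainly through social media with online registration, reminders are automated, delivery is assigned to others, and a second analyst is listed.
- A reader might infer that unblinded self-report defeats the blinded analysis, or biases results by a known amount in a known direction. Participant unblinding is openly disclosed and does not prevent a blinded analysis. The protocol gives no basis for the size or direction of any expectation effect.

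**Conclusion.** Wrong as written, within limits. If days waiting enters the primary analysis, the promise of a blinded primary analysis fails for the therapist-guided arm and so for two of the three pairwise contrasts. The blind between app and assessment-only is not broken by this variable. The conclusion rests on two assumptions: that the covariate sentence covers the primary analysis, and that waiting time is zero or missing outside the therapist arm, as the text implies. The resulting bias cannot be quantified from the document. The overlap of roles is a separate, lesser risk to the blind that can be removed with staff already listed. The single-blind wording is unclear rather than false: read with the rest of its paragraph, it can only mean the analyst, and it should say so.

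**What to change.** 1. Reconcile the DESIGN and INTERVENTIONS statements. Take days waiting out of the blinded primary model and use it only in a secondary analysis within the therapist-guided arm, after the primary analysis is locked.
2. Give the primary analyst a file with coded arms and without arm-specific variables: days waiting, session attendance, app usage and CSQ-I. Release these after lock.
3. Have the primary analysis run by the analyst already listed in Table 3 who has no recruitment or follow-up duties.
4. Describe the trial as open-label with self-reported outcomes and a blinded analyst.

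The cost should be stated openly: the primary model loses a covariate that the protocol currently says will be included, and arm-specific exposure analyses come slightly later. The rest is wording, a two-step data release and an allocation of tasks among existing staff.

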- **Assessment-only:** All assessments will be conducted, but no intervention will be provided to this group. The assessment only condition is necessary for investigating natural trajectory and form the baseline level for assessing risk reduction in the interventional groups.

Figure 1. Screenshot from GooglePlay of the “Tankevirus” smartphone app.

All interventions and assessments for all trial arms will be fully digitalized through a research app, which is essentially a modification to the already developed “Tankevirus”-app, including all preassessments and follow-ups. Human interaction is limited to the therapist-led group, otherwise automated nudges and notifications will remind the adolescents to complete assessments. This will be beneficial when considering the scalability and implementation of the intervention, should it be successful, and for evaluating whether human interaction indeed is a driver of the effect between interventions.

HYPOTHESIS: The main hypothesis is that the outcome related to the therapist-guided group intervention will be more effective in reducing number of relapses and time to relapse during the follow-up period when compared to the app-based approach, and that the app-based approach will be more efficacious compared to an assessment-only condition/care-as-usual (the control group).

PARTICIPANTS: Participants will primarily be recruited through large scale marketing campaign in social media (i.e., TikTok, Snapchat, Instagram) and web pages of user organizations, informing about this trial and the opportunity to take part. This is the most efficient way of reaching eligible participants, as clinicians seldom refer to such a trial ([name], PI of the StayFine-trial targeting adolescents in remission, *personal communication*, 21.07.24). Overall, 90 % of Norwegian adolescents are on social media (30). Currently, we have established contact with the social media coordinator in Mental Helse Ungdom. We will also post physical adds at places we expect adolescents to see them. Through other ongoing projects we have contact with ~150 general practitioners and we have established a collaboration with the low-threshold service UngArena.

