STATISTICAL POWER: For the primary endpoint investigating number of relapses within the follow-up period, we will conduct a fixed effects omnibus ANOVA. Presuming Cohen's $f = .25$, alpha = .0167 (.05/3; Bonferroni corrected) and power = .8 including three groups, we will require a total sample size of 207 (GPower 3.1). Presuming 15 % dropout, we will need 238 adolescents to take part in the study. For time to relapse, the power analysis was performed using Monte Carlo simulation. A large pool of simulated survival data was generated, reflecting a hazard ratio of 0.6 between two groups, a 15% annual dropout rate with competing risk, and a 1-year observation period. The simulation titrated the sample size, drawing 10.000 random samples at each step and fitting Cox proportional hazards models. Power was estimated as the proportion of samples yielding statistically significant results at the 0.05 level. The analysis concluded that approximately 165 individuals per group, meaning that a total of 495 adolescents would be required to achieve 80% power for detecting a hazard ratio of 0.6 under the specified conditions. This simulation method accounts for the complexities of survival data, including censoring and limited observation time, providing a robust sample size estimate for the study design. All randomized participants will be subjected to analysis in accordance with an intention to-treat approach. The multiarmed parallel group randomized trial will be reported according to the extensions recommended by CONSORT (44).

RISK: Recruitment is the main risk factors of this trial. A few trials are currently under way in adolescent populations (e.g., StayFine trial (16), RuMeChange (15)) and in the first, they were in contact with 3018 adolescent during a three-year period. Their strict inclusion criteria and elaborate pre-inclusion assessments hindered several from participating, but still they had 589 eligible

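### The power calculation makes no allowance for clustering in the therapist-led group arm, so the stated 80% power is too high for both guided time-to-relapse contrasts if outcomes correlate within groups or therapists

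*Protocol*

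**What the plan says.** All references are to protocol section 1.3.

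- **Delivery (Interventions).** Therapists give the guided programme by webinar, with chat, in "3 weekly 75-minutes sessions to groups of approximately 30-35 participants". Participants book a time slot, and "a certain waiting period (~1 week) must be expected"; days waited will enter the analysis as a covariate.
- **Other arms (Interventions).** "Human interaction is limited to the therapist-led group". The app and assessment-only arms are individual.
- **Time to relapse (Statistical power).** A Cox simulation "reflecting a hazard ratio of 0.6 between two groups, a 15% annual dropout rate with competing risk, and a 1-year observation period" led to "approximately 165 individuals per group, meaning that a total of 495 adolescents would be required to achieve 80% power". The text adds: "This simulation method accounts for the complexities of survival data, including censoring and limited observation time".
- **Number of relapses (Statistical power).** Here "we will conduct a fixed effects omnibus ANOVA", with 207 participants before dropout at f = .25 and alpha .0167.
- **Blinding (Design).** "The primary endpoint of the trial will be analyzed blinded to treatment allocation".

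No ICC, design effect, group term, therapist term or number of therapists is stated anywhere in the protocol.

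**The concern.** Participants are randomised individually, but those in the guided arm then share a session, a chat and a therapist. This is a partially nested design: 165 guided participants make about five groups of 33, while the other 330 participants are independent. If outcomes within a group or under one therapist are even slightly alike, the guided arm carries less information than 165 independent people.

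Two things follow. Both contrasts involving the guided arm have less power than stated. Tests that treat everyone as independent, including the announced ANOVA, reject too often. Guided versus app is the first half of the main hypothesis, and the protocol wants to learn whether human contact drives the effect. A result produced by a few groups or therapists could be mistaken for an effect of guidance. A later SAP can choose the model, but the 80% and the 495 are fixed here.

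**Working it through.** **1. The plan's own figures.**
- *ANOVA.* Noncentral F with 3 groups, f = .25 and alpha .05/3 gives 80.5% power at N = 207. The figure therefore reproduces under full independence. At N = 495 the power is 99.7%.
- *Time to relapse.* The 165 cannot be fully reproduced because no control relapse risk is given. Schoenfeld's formula needs 4(1.96 + 0.84)²/(ln 0.6)² ≈ 121 events. With exponential relapse and 15% annual dropout, 330 people yield 121 events (72.4 + 48.6) at a control 12-month risk of about 47%. A Cox simulation with independent patients gave 78% power at a risk of 45% and 83% at 50%. So 165 per arm is consistent with 80% power and no clustering term.

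**2. Adding clustering in the guided arm only.** ICC values are assumed. With group size m:
- design effect in the guided arm: DE = 1 + (m − 1) × ICC
- average over the two arms of a guided contrast: A = (DE + 1)/2
- power = Φ(2.80/√A − 1.96)
- type I error if groups are ignored = 2[1 − Φ(1.96/√A)]

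Example, m = 33 and ICC 0.02: DE = 1 + 32 × 0.02 = 1.64; A = 1.32; power = Φ(2.80/1.149 − 1.96) = Φ(0.48) = 68%; type I error = 2[1 − Φ(1.706)] = 8.8%.

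| m | A at ICC 0.01 / 0.02 / 0.05 | Power (stated 80%) | Type I error if ignored (nominal 5%) |
|---|---|---|---|
| 33 | 1.16 / 1.32 / 1.80 | 74 / 68 / 55% | 6.9 / 8.8 / 14.4% |
| 20 | 1.095 / 1.19 / 1.475 | 76 / 73 / 64% | 6.1 / 7.2 / 10.7% |
| 10 | 1.045 / 1.09 / 1.225 | 78 / 77 / 72% | 5.5 / 6.0 / 7.7% |

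**3. Few groups.** With k groups, Satterthwaite df = (DE + 1)²/[DE²/(k − 1) + 1/164], used in a noncentral t.
- Five groups of 33: df 12.2 / 10.3 / 7.6, power 67 / 60 / 45%. At ICC 0 the same formula gives df 15.6 and power 75%, so about 5 points of each loss come from the degrees of freedom and not from correlation.
- Sixteen groups of about 10: df 51 / 48 / 41, power 77 / 75 / 70%.

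**4. Checks by simulation.**
- *Cox*, five groups of 33, control risk 51%, unclustered power 82–83%. With a between-group SD of 0.2 on the log hazard (ICC about 0.014), power against the true standard error was 71%, and a Cox test ignoring groups had about 9% type I error. At SD 0.3 (ICC about 0.03) the figures were 57% and 13%.
- *Log-rank ignoring groups*, SD 0.14 to 0.32, control risk 30–50% (assumed). Type I error ran from 6–7% up to 11–14% at 33 per group, and from 5% to 8% at 10 per group.
- *Announced ANOVA*, nominal 1.67%, 165 per arm, ICC 0.01 / 0.02 / 0.05. At 33 per group, type I error was 2.9 / 3.5 / 6.8% (5,000 runs) and 2.5 / 3.7 / 7.4% in a repeat with 20,000. At 10 per group it was 1.8 / 1.8 / 3.2% and 1.7 / 2.0 / 2.9%. Power stayed at about 99%.

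**5. How large will groups be?** Filling groups of 33 within about a week needs 33 guided, hence about 99 randomised, per week. That would enrol 495 in 5 weeks. If enrolment instead took 52 weeks (assumed), 165/52 = 3.2 guided participants arrive per week and one group takes 33/3.2 ≈ 10 weeks to fill. The stated group size and the stated wait fit together only under very fast recruitment, so smaller groups are a real possibility.

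**6. Therapists.** Their number is not given. If four shared the arm (41 each, assumed) and the ICC were at therapist level, A = 1.20 / 1.40 / 2.00 and power is about 72 / 66 / 51%.

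**The case against.** The strongest reply is that every loss depends on an ICC the protocol does not give, and that it may be small. The intervention is three webinars, participants are anonymous to each other, and relapse is self-reported over 12 months. Groups may be smaller than planned, non-attenders kept under intention-to-treat share no group, and nothing says the same people stay together for all three sessions. With groups of 10 and an ICC of 0.01–0.02 the loss is only 2 to 3 points, and ANOVA type I error is barely above nominal. All of this stands, and it points to the low end of the range. It does not make the ICC zero: anonymity among participants does not remove a shared therapist or session, and at the protocol's own group size an ICC of 0.01 costs about 6 points.

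A second reply is that model terms belong in the SAP, that no final time-to-relapse model is announced, and that 80% is claimed for two unnamed groups. The first two points are fair, and no fault is found here with an unannounced Cox analysis. But the power figure sets the size of all three arms, so it covers the guided contrasts, and the ANOVA is announced. The list of what the simulation covers need not be exhaustive, yet no clustering input appears among its stated assumptions.

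Third, small-sample inference itself costs about 5 points with five groups, and a variance from so few groups is poorly estimated. That is correct, and it belongs in the restated power.

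**Conclusion.** The concern holds, conditional on an ICC above 0. The stated 80% is then too high for guided versus app and guided versus assessment-only. At an assumed ICC of 0.01 to 0.05, power is about 74% down to 55% with groups of 33 and 78% down to 72% with groups of 10, before any small-sample correction. These figures take 80% under independence as the starting point, which is plausible but cannot be confirmed without the control relapse risk. The low end is the more likely. Confidence in the size is therefore moderate; that the design is partially nested with no stated allowance is clear. App versus assessment-only is unaffected. The ANOVA's power is not in question, only its type I error.

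**What to change.** 1. Record session group and therapist for every guided participant from the start. The platform is meant to hold anonymised data, so these may be hard to recover later.
2. Name a partially nested analysis for the guided contrasts: a session-group random effect in the guided arm only (frailty for time to relapse, random intercept for number of relapses), with app and control participants as singletons and small-sample inference.
3. If there are too few therapists to estimate a variance, report results by therapist and leaving one therapist out, and state that the guided effect is conditional on these therapists.
4. Address blinding. A group identifier reveals the guided arm, and so does the waiting-days covariate, because a wait is expected only there. Either have someone outside the blinded team run the pre-written model, or state that the blind holds only between app and control.
5. Restate power for the guided contrasts at 165 per arm over a stated range of ICC and group size, showing separately what the degrees of freedom cost.

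The cost is two identifier variables, one model term, a sentence on blinding and a rerun of the simulation. No extra enrolment is required, but this reports the shortfall and does not remove it. Restoring 80% at 33 per group with equal arms would take 165 × A, about 192, 218 or 297 per arm at ICC 0.01, 0.02 or 0.05, before the small-sample correction. Guided-arm intervals will be wider, and the between-group variance will be imprecise if groups are few.
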